9.7. Exposure In Utero During Clinical Studies

DS must be notified of any female subject or any male subject whose female partner becomes pregnant while receiving or within 90 days of discontinuing the study drug. Reporting after follow-up visit or early termination is done voluntarily by the Investigator.

Although pregnancy is not technically an AE, all pregnancies must be followed to conclusion to determine their outcome. This information is important for both drug safety and public health concerns. It is the responsibility of the Investigator or designee to report any pregnancy in a female subject or a male subject's female partner using the Exposure In Utero (EIU) Reporting Form. Please contact your study monitor to receive the EIU Reporting Form upon learning of a pregnancy. The Investigator should make every effort to follow the subject until completion of the pregnancy and complete the EIU Reporting Form with complete pregnancy outcome information, including normal delivery and induced abortion. The adverse pregnancy outcome, either serious or nonserious, should be reported in accordance with study procedures. If the outcome of pregnancy meets the criteria for immediate classification as an SAE (ie, postpartum complications, spontaneous or induced abortion, stillbirth, neonatal death, or congenital anomaly, including that in an aborted fetus), the Investigator should follow the procedures for reporting SAEs outlined in Section 9.5. For reports of pregnancy in the female partner of a male subject, the EIU Reporting Form (or SAE form if associated with an adverse outcome) must be completed with the subject's enrollment number, initials, and date of birth, and details regarding the female partner should be entered in the narrative section.

9.8. Overdose

Overdose, defined as the accidental or intentional administration of any dose of pexidartinib that is considered both excessive and medically important. All occurrences of overdose must be reported to (CRO or Sponsor) within 24 hours of awareness. Overdose could be reported via

[SAVER/overdose] form or eCRF. An "excessive and medically important" overdose includes any overdose in which either a SAE, a non-SAE, or no AE occurs and is considered by the Investigator as clinically relevant, i.e. poses an actual or potential risk to the subject. Details of the overdose including pexidartinib dosage, clinical course, associated AEs, and outcome must be captured in the Narrative form of the eCRF within electronic data capture (EDC).

9.9. Clinical Laboratory Evaluations

Clinical laboratory evaluations will be performed in local laboratory at the study visits indicated in the Schedule of Assessment (Table 16.3). For clinical laboratory parameters, the reference range of the institution that performs the measurement will be used.

Clinical laboratory evaluations will be performed as outlined below:

Blood samples for analysis of the following clinical chemistry, hematologic, coagulation, and hormone testing will be obtained:

Clinical Chemistry

• Sodium	• Total protein
Potassium	• Albumin
• Chloride	• Triglycerides [*]
• CO ₂	• Total cholesterol [*]
• Calcium	• HDL-cholesterol [*]
Phosphorus	• LDL-cholesterol*
• Glucose [*]	• Uric acid
Blood urea nitrogen	Lactate dehydrogenase
• Creatinine (creatinine clearance)**	

 CO_2 = Carbon dioxide; HDL = high density lipoprotein; LDL = low density lipoprotein * Fasting is recommended but not required.

**CLcr will be calculated using following formula (Cockcroft-Gault).

 $CLcr = \{((140 - age) \times weight (kg))/(72 \times serum creatinine (mg/dl))\} (\times 0.85 \text{ if female}).$

Liver function Tests

Alkaline phosphatase	Total bilirubin
• AST	Direct bilirubin
• ALT	• GGT

ALT = alanine aminotransferase; AST = aspartate aminotransferase. ; GGT = gamma-glutamyl transpeptidase.

Hematology

Red blood cell count	Hemoglobin
• White blood cell count with differential	• Hematocrit
Platelet count	

Hepatitis Panel

Hepatitis B virus surface antigen test and hepatitis C virus antibody test

Coagulation

Prothrombin time, activated partial thromboplastin time, and INR

Hormone Testing

Females	Males
• FSH	• FSH
• LH	• LH
Progesterone	• Testosterone
Estradiol	

FSH = follicle stimulating hormone; LH = luteinizing hormone

Urinalysis (dipstick and microscopic analysis)

Urine samples will be obtained for analysis of the following parameters:

• pH	٠	Ketones/acetone
• Protein/albumin	•	Hemoglobin/blood
• Glucose/sugar	•	Red blood cells, white blood
Nitrites		cells, epithelial cells, bacteria,
		casts, crystals

Others

Serum sample must be collected for AMA at Screening and once severe hepatotoxicity is observed (Section 5.4).

9.10. Pregnancy Test

For women of childbearing potential only, a serum pregnancy test (β -human chorionic gonadotropin) will be performed at the study visits indicated in the Schedule of Assessment (Table 16.3).

For postmenopausal subjects (no childbearing potential, as indicated by an elapse of at least 12 months after the last menstruation) or female subjects who have no possibility of pregnancy due to sterilization surgery, etc. the pregnancy test will not be required.

Female subjects who have been amenorrheic for 12 months or longer due to medical reasons other than sterilization surgery (eg, effect of medication) will be regarded as women of childbearing potential and are required to undergo the pregnancy test.

9.11. Vital Signs

Vital signs, including systolic/diastolic BP, pulse rate and temperature will be measured in accordance with institutional standards and generally must be performed before any invasive procedures, eg, blood withdraws. Vital signs and weight will be measured at the study visits mentioned in the Schedule of Assessment (Table 16.3). Height will be measured at the Screenings visit only.

BP and pulse rate will be measured after the subject has rested in a recumbent position for 5 minutes or more.

Information will be entered in the eCRF on whether or not measured, date of measurement, and measurement results.

9.12. Electrocardiograms

A standard 12-lead ECG will be obtained at the study visits indicated in the Schedule of Assessment (Table 16.3).

Subjects should rest in the supine position for at least 5 minutes before the ECG recording is started. The ECG recordings must be performed using a standard high-quality and high-fidelity electrocardiography machine equipped with computer-based interval measurements. For safety monitoring purposes, the ECGs must be reviewed, signed, and dated promptly by a qualified Investigator (or Investigator's assistant, nurse practitioner) and any clinically important finding must be recorded on the appropriate eCRF. The Investigator is responsible for interpreting all ECGs. The results will include heart rate, RR interval, PR interval, QRS interval, QT interval, and QTcF interval.

At the visits when ECGs are to be performed, subjects must be told NOT to take the morning dose of study drug; instead, they must be told to bring their bottle of study drug to the site and take the morning dose upon instruction by the site staff.

Whether or not measurement is performed, date performed, results, and findings for the parameters will be recorded in the eCRF.

9.13. Examinations

The examination will be performed by a qualified individual such as the Investigator at the study visits indicated in the Schedule of Assessment (Table 16.3).

Physical examination findings will be used to evaluate the following systems or areas: general appearance, oral cavity and neck, cardiothoracic, dermatologic, abdominal, musculoskeletal, and neurological.

9.14. Safety Monitoring

9.14.1. Safety Monitoring Committee

A safety monitoring committee (SMC) to assess liver toxicity will be established and will be responsible for safeguarding the interests of study subjects, assessing the safety of the interventions during the study, and monitoring the overall conduct of the study. The SMC will

also evaluate progress of the study and other relevant information, and make recommendations about continuing, modifying, or stopping the study. A separate SMC Charter will define the SMC membership, its roles and responsibilities, and the process for providing feedback to the DS.

9.14.2. Hepatic Adjudication Committee

An external hepatic adjudication committee (HEAC) is used for evaluating hepatic AEs for this study. Details on the membership, responsibilities, and working procedures of the external HEAC will be described in the separate charter. This additional data collection will cover a more in-depth, relevant medical history, diagnostic evaluation, treatment, and outcome of the event. Adjudication of hepatic events will be based on evaluation of eCRFs and source documents, including, but not limited to, liver ultrasound, other imaging of the liver, and liver biopsy.

10. STATISTICAL METHODS

10.1. Analysis Sets

10.1.1. Enrolled Analysis Set

The enrolled analysis set will include all subjects who sign the ICF and are enrolled in the study.

10.1.2. Full Analysis Set/Safety Analysis Set

The Full analysis set (FAS)/safety analysis set will include all subjects who received at least 1 dose of pexidartinib.

10.1.3. Per-protocol Analysis Set

Not Applicable.

10.1.4. Pharmacokinetic Analysis Set

The PK analysis set will include all subjects in the enrolled analysis set who received at least 1 dose of pexidartinib and had measurable plasma concentrations of pexidartinib.

10.1.5. Pharmacokinetic Analysis Set for Noncompartmental Analysis

The PK analysis set for noncompartmental analysis will include all subjects in the PK analysis set who chose Schedule 1 in clinical sites.

10.2. Procedures for Handling Missing, Unused, and Spurious Data

For the primary efficacy analysis as well as for all analyses of responder proportion endpoints performed on the FAS, subjects who do not provide data for the responder endpoint will be considered nonresponders, ie, assigned to the less favorable outcome for the endpoint. Subjects who do not have the Week 25 MRI assessment, for example, those who discontinue the study without Week 25 assessment will be considered nonresponders.

10.3. General Statistical Considerations

The data cutoff for the primary analysis will occur after all subjects have either discontinued the study or completed at least Week 25 assessments.

Continuous variables will be summarized by the number of observations, mean, standard deviation, median, 25th and 75th percentile, and minimum and maximum values. Categorical variables will be summarized using frequency counts and percentages.

Assessments of change from baseline to post-treatment or the ratio of post-treatment to baseline will include only those subjects with both baseline and post-treatment measurements. The last nonmissing value of a variable taken before the first dose of study drug will be used as the baseline value, unless otherwise specified. In general, missing or dropout data will not be imputed for the purpose of data analysis, unless otherwise specified.

For the primary efficacy endpoint and secondary efficacy endpoints with the exception of duration of response, point estimate and accompanying 95% CI will be computed. For duration

of response, Kaplan-Meier product limit methodology will be utilized to provide estimates, including those for the median and 25th and 75th percentiles.

10.4. Study Population Data

Subject disposition will be summarized for subjects in the enrolled analysis set. The total number of subjects for each defined analysis population will also be tabulated. The demographic and baseline characteristics will be summarized descriptively for the FAS/safety analysis sets. Study drug exposure and study duration will be summarized using descriptive statistics for the safety analysis set.

10.5. Efficacy Analyses

10.5.1. Primary Efficacy Analyses

The primary endpoint will be the proportion of subjects who achieve a CR or PR of pexidartinib based on RECIST 1.1 at Week 25 by centrally reviewed MRI scan (see Section 7.1). The primary analysis will be completed using the FAS. The estimate of the proportion and two-sided 95% CI based on Clopper-Pearson method will be provided.

10.5.2. Secondary Efficacy Analyses

The secondary efficacy endpoints to be analyzed at Week 25 include:

- Proportion of subjects who achieve a CR or PR of pexidartinib based on TVS at Week 25 by centrally reviewed MRI scan
- Mean change from baseline in range of motion of the affected joint, relative to a reference standard for the same joint, at the Week 25
- Mean change from baseline score in the PROMIS Physical Function Scale at the Week 25

Subjects who do not provide data for the endpoint will be considered to be non-responders (TVS).

The estimate of the proportion of TVS responders (ie, those who achieve a CR or PR based on TVS criteria) and 95% CI at Week 25 will be calculated.

Other secondary endpoints will be also summarized with point estimates and 95% CIs.

For the endpoint of range-of-motion, raw measurements of the affected joint will be performed using a goniometer and expressed in degrees (Section 7.2.1). The value for a given joint will be normalized to a reference standard, ie, full range of motion for the same joint, to provide a relative value. The reference standard will be derived from American Medical Association disability criteria.¹²

Duration of response will also be analyzed as a secondary endpoint and will be summarized for responders based on (i) RECIST 1.1 and (ii) TVS. Duration of response is defined from the date of the first recorded response to the first date of documented disease progression. For subjects who do not have radiological progression, the duration of response will be censored. The Kaplan-Meier product limit method will be used to compute the estimate and 95%CI of the
median and 25th and 75th percentiles. The number of responders, the number with subsequent disease progression, and the number with censored values will be displayed as well. Within the framework of Kaplan-Meier methodology, the estimates for proportions of responders with response durations longer than 3, 6, 12, 18, and 24 months will also be provided.

The percentage and 95% CI will be provided for the best overall response in the order of CR, PR, SD, PD, and NE.

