1.4. Study Rationale

The current study will be a multicenter, single arm Phase 3 study in Asian subjects with symptomatic TGCT associated with severe morbidity or functional limitations and not amenable to improvement with surgery. The subject population to be studied in this study will be the almost same as in the PLX108-10 study.

The primary endpoint in this study is the proportion of subjects who achieve a complete response (CR) or partial response (PR) based on centrally read MRI responder criteria as defined by RECIST 1.1 at Week 25, the same as that defined in the PLX108-10 study. The MRI will be assessed at every 12 weeks. A subject will be considered to have a response if the tumor meets the criteria for response and has a documented nonprogression at Week 25. To minimize bias and reduce variability from this single arm study, centralized review of the MRI will be performed by the blinded readers. The Imaging Charter for this study describes the image acquisition standards and methodology to be used as well as the standards for image interpretation.

The secondary endpoints are: (i) response based on tumor volume score (TVS) at Week 25; (ii) range of motion at Week 25; (iii) Patient-reported Outcomes Measurement Information System (PROMIS) Physical Function Scale at Week 25; (iv) best overall response; (v) duration of response; (vi) safety; and (vii) PK.

The endpoint of TVS by the use of central MRI readers will be reinforced for the primary imaging endpoint of RECIST 1.1 assessment. The endpoint of PROMIS assessment or improvement of range of motion will reinforce the explanation of clinical benefit from primary imaging endpoint.

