7.1. Primary Efficacy Endpoint

The primary endpoint will be the proportion of subjects who achieve a CR or PR of pexidartinib based on RECIST 1.1 at Week 25 by centrally reviewed MRI scan.

The RECIST 1.1 response categories are defined by the following criteria:

- Complete Response (CR) Disappearance of all tumors.
- **Partial Response (PR)** At least a 30% decrease in the sum of diameters of target tumors, taking as reference the baseline sum diameters.
- **Progressive Disease (PD)** At least a 20% increase in the sum of diameters of target tumors, using the smallest sum on study as the reference. In addition to the relative increase of 20%, the sum must also demonstrate an absolute increase of at least 5 mm. The appearance of one or more new tumors is also considered progression.
- **Stable Disease (SD)** Neither sufficient shrinkage to qualify for PR nor sufficient increase to qualify for PD.

CR and PR will define response for the primary endpoint and additional efficacy analyses.

Determination of an overall response for each time point is based on the combination of responses for target lesions, and the presence or absence of one or more new lesions. For the purpose of this protocol and in alignment with RECIST 1.1, determination of the tumor response status for each subject within 24 weeks treatment with respect to the primary efficacy endpoint is shown in Table 7.1.

To be considered a response, a tumor must meet the criteria for response and must have documented non-progression at Week 25. A tumor that achieves PR at Week 13 followed by neither sufficient shrinkage to qualify for CR nor sufficient increase to qualify for PD (ie, non-CR/non-PD/not evaluable [NE]) at Week 25 will be considered a responder for the primary efficacy endpoint.

Time Point Response at Week 13 (C4D1 visit)	Time Point Response at Week 25 (C7D1visit)	Tumor Response Status (Primary efficacy endpoint)
CR or PR	CR	Response (CR)
CR or PR	PD	Nonresponse (PD)
PR	non-CR/non-PD/non-NE ^a	Response (PR) ^b
SD	CR or PR	Response (CR or PR)
SD	SD	Nonresponse (SD)
SD	PD	Nonresponse (PD) ^c
CR, PR, SD, or NE	NE	Nonresponse (NE)
PD	Any	Nonresponse (PD)
NE	CR or PR	Response (CR or PR)
NE	SD or PD	Nonresponse (SD or PD)

 Table 7.1:
 Definitions of Response for the Primary Endpoint

CR = complete response; NE = not evaluable; PD = progressive disease; PR = partial response;

SD = stable disease

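### Does the duration-of-response summary leave out subjects who respond at Week 13 and progress by Week 25?

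*Combined protocol and SAP*

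**What the plan says.** Section 10.5.2 states that duration of response "will be summarized for responders based on (i) RECIST 1.1 and (ii) TVS". It continues: "Duration of response is defined from the date of the first recorded response to the first date of documented disease progression". On censoring it says: "For subjects who do not have radiological progression, the duration of response will be censored". Kaplan-Meier proportions are planned at 3, 6, 12, 18 and 24 months. The paragraph does not define responders.

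Section 7.1 has two statements about response. One is broad: "CR and PR will define response for the primary endpoint and additional efficacy analyses". The other carries a Week 25 condition: "To be considered a response, a tumor must meet the criteria for response and must have documented non-progression at Week 25". The sentence after it describes a subject who "will be considered a responder for the primary efficacy endpoint". Section 1.4 repeats the condition while describing the primary endpoint: "A subject will be considered to have a response if the tumor meets the criteria for response and has a documented nonprogression at Week 25". Table 7.1 classes CR or PR at Week 13 followed by PD at Week 25 as nonresponse, and likewise when Week 25 is not evaluable. Section 7.2 applies similar logic to the TVS status within 24 weeks.

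Section 10.2 treats subjects without data as nonresponders in the primary analysis, "as well as for all analyses of responder proportion endpoints performed on the FAS", and names subjects with no Week 25 MRI as an example.

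**The concern.** The only responder rule the protocol spells out looks ahead to Week 25, while the duration clock can start at Week 13. If a programmer carried a Table 7.1 responder flag into the duration analysis, the shortest responses (PR at Week 13, PD at Week 25) would leave the set. Every Week 13 responder who stayed would be free of documented progression for at least one scan interval by construction. This is guarantee-time bias: the Kaplan-Meier curve is flat at the start because of how the set was chosen.

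The 3-month landmark would be affected most, since it falls just after the first 12-week scan interval. The effect would also be visible at the primary cutoff, which comes once all subjects have discontinued or completed Week 25. For the last-enrolled Week 13 responders, Week 13 to Week 25 may be the only interval yet observed.

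Two further exclusions would follow from the same reading: subjects first responding after Week 25, and Week 13 responders with no Week 25 MRI. The Section 10.2 rule might also be thought to turn a Week 13 PR with no Week 25 scan into a nonresponse for best overall response.

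**Working it through.** **The plan's own figures.** Section 10.11 gives exact 95% intervals for 9 to 16 responders out of 35. Clopper-Pearson limits reproduce all eight rows; for example, 13/35 = 37.1% (21.5%, 55.1%). The plan states no figure for duration of response, so what follows is illustration.

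**Inputs.** The scan interval is 12 weeks (Section 1.4), which is 84 days, or 84/30.44 = 2.76 months. The illustrative number of responders is 13, from the 37.7% Week 25 rate in PLX108-10 (Section 1.3.2): 0.377 × 35 = 13.2. Two quantities have no source in the documents and are assumed: the share *w* of responders first seen at Week 13, and the risk *q* of PD per 12-week interval.

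**If the Week 25 status were used: counts.** Take 13 Week 25 responders and *k* subjects with response at Week 13 and PD at Week 25, with no other event by 3 months. Excluding the *k* gives 100% beyond 3 months. Including them gives 13/(13 + *k*):

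| *k* | Proportion beyond 3 months |
|---|---|
| 1 | 92.9% |
| 2 | 86.7% |
| 3 | 81.3% |

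Each subject moves the estimate by about 5 to 7 points.

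**If the Week 25 status were used: rates.** The set kept is *w*(1 − *q*) + (1 − *w*) = 1 − *wq* of all responders, and 1 − *q* of all responders are event-free at 3 months. The restricted estimate is therefore (1 − *q*)/(1 − *wq*) against a true 1 − *q*. With *w* = 0.6:

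| *q* | Restricted | All responders |
|---|---|---|
| 5% | 0.95/0.97 = 97.9% | 95% |
| 10% | 0.90/0.94 = 95.7% | 90% |
| 15% | 0.85/0.91 = 93.4% | 85% |

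At 6 months with *q* = 10%, it is 0.81/0.94 = 86.2% against 81%. If every response began at Week 13 (*w* = 1), the 3-month overstatement would equal *q*.

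**Effect on the median.** With exponential durations and all first responses at Week 13, assumed true medians of 6, 12, 24 and 48 months become 8.8, 14.8, 26.8 and 50.8. The shift is one scan interval, about 2.8 months. If half first respond at Week 13, the medians become 7.3, 13.3, 25.4 and 49.4.

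**Number of subjects involved.** Taking 13 as all responders and *w* = 0.6, the number removed is 13 × 0.6 × *q* = 0.4, 0.8 or 1.2 at *q* = 5%, 10% or 15%.

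**If any CR or PR admits a subject.** Nobody is removed and the bias is zero.

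**Which reading the text supports.**
- The Week 25 condition in Section 7.1 follows a paragraph limited to the primary efficacy endpoint. The next sentence names that endpoint again, as do the title and status column of Table 7.1.
- The sentence that extends beyond the primary endpoint says only CR and PR, with no Week 25 condition.
- Section 3.1.2.2 qualifies duration of response with CR or PR in parentheses, exactly as it does best overall response, which is an any-time endpoint.
- Section 10.5.2 lists three endpoints for Week 25 (TVS response, range of motion, PROMIS). Duration of response is introduced separately. Section 10.5.3 expressly excepts duration endpoints from Week 25 analysis.
- Starting from the first recorded response is time-point language, and needs only a CR or PR at some scan.

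**The other exclusions.** A Week 13 responder with no later scan would be censored with essentially no follow-up, so keeping or dropping that subject hardly changes the curve. Leaving out late first responders could move the estimate either way. For best overall response, a subject with a Week 13 PR has supplied data, so the Section 10.2 rule for absent data does not naturally apply. That endpoint is also reported across CR, PR, SD, PD and NE, which gives missing assessments their own category.

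**The case for a change.** The best case for a change is that the duration paragraph does not define its population and that the only explicit responder rule nearby is the biased one. The other mention of responders in Section 10.5.2, for TVS, sits in a sentence about Week 25. Two readings give two Kaplan-Meier curves in an open-label single-arm study. With about 13 responders even one reclassified subject shows, and a choice not fixed beforehand could be made after the data are seen. A clarifying sentence would cost almost nothing.

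The word is indeed undefined, and the bias under the Week 25 reading is real and runs in the stated direction. But the readings are not evenly supported: the Week 25 rule is tied each time to the primary endpoint, and the duration wording points to any CR or PR. In the TVS sentence, Week 25 attaches to the estimated proportion; responders there are simply those achieving CR or PR by TVS. Section 10.12 also leaves efficacy definitions to a separate SAP, to be finalised before database lock. That text is not part of the document reviewed and may settle the point.

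**Conclusion.** No change is called for. The plan does not restrict duration of response to Week 25 responders. It leaves one word undefined, and an analyst would ordinarily fill it with any centrally read CR or PR, for which the bias is zero.

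The 5 to 7 points per excluded subject at 3 months, and the shift of up to about 2.8 months in the median, arise only if the primary-endpoint status is carried into this analysis. The first assumes about 13 responders; the second assumes exponential durations. The expected number of subjects affected, about one or fewer, rests on an assumed 60% Week 13 share and assumed progression risks of 5% to 15% per interval. Section 1.3.1 reports that many Phase 1 responders stayed on treatment for more than 2 years, which suggests, without proving, that early progression is uncommon. The summary is descriptive, with no test or decision rule attached.
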